
Given our prior experience⁵⁴ and proposed techniques, we conservatively project an 80% retention rate at 6 months.

Outcome Measures. Primary outcomes will be caregiver prolonged abstinence and 7-day point prevalence of tobacco use at 6-weeks and 6-months. Secondary caregiver outcomes will include cigarettes smoked, quit attempts, readiness to quit, and use of NRT and cessation resources (QL, smokefreeTXT, smokefree.gov). Child outcomes will be presence or absence of total home/car smoking bans, reported SHSe, and number of SHSe-related PED visits and hospitalizations at CCHMC.

Baseline Assessment. (Table 1) The brief baseline assessment (T0) will be conducted using a self-administered electronic survey to be completed on a tablet computer. The assessment items chosen are empirically validated measures from studies conducted with low-income disadvantaged study populations.^{42,66-71,39,63-68} The items are brief, easily comprehensible, and take into account low literacy levels. They are as follows:

Table 1: Measures for Baseline and Follow-up Assessments by Assessment Point	T0	T1	T2
Demographics; Financial Strain, , Household Smokers,	✓		
Tobacco Use History, Nicotine dependence, , Motivation to Quit	✓	✓	✓
Risk Perceptions: Child; Benefits of Quitting: Child	✓	✓	✓
Child's SHSe, , Child SHSe - related PED visits or Hospitalizations	✓	✓	✓
Healthy Habits Lifestyle- daily: fruits/vegetables, screen time, exercise, sugary drinks	✓	✓	✓
SBIRT and HHC Satisfaction,	✓		
Prolonged abstinence, point prevalence, nicotine dependence, readiness to change, quit attempts		✓	✓
Cessation Resource utilization: NRT, QL, SmokefreeTXT, Smokefree.gov, or other resources	✓	✓	

1. Demographics and tobacco use. We will collect gender, age, race/ethnicity, level of education, employment status, , number of cigarettes smoked daily, time to the first cigarette of the day, nicotine dependence, number of attempts to quit >24 hours, use of pharmacological and/or behavioral treatments for quitting, motivation to quit using the Contemplation Ladder, and stage of change in readiness to quit.^{41,72} Questions will also be asked about marijuana use by the participant and household members; participants will not be required to answer these questions. Participants who consented prior to Version 11 of the protocol may be re-consented at follow-up such that we may obtain information about marijuana use.

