We will use GLMM to evaluate the relative effectiveness of the SBIRT versus HHC group on our primary outcomes: point prevalence and prolonged abstinence at 6-months. The analysis will be repeated with caregiver level differences between groups included as covariates. We will use mixed model analysis of covariance, with repeated measures to assess change (controlling for baseline differences between groups) to assess the effect of the SBIRT on secondary outcomes including reduction in use, number of quit attempts, and changes in readiness to quit. Kappa statistic will be used to assess agreement between the caregiver's self-report and the assessment of tobacco use based on expired carbon monoxide levels and/or salivary cotinine at 6 months. It is possible that use of and adherence to the NRT will influence outcomes in the intervention group. In addition, some of the participants in the control condition may obtain NRT during the study interval. We will examine NRT use or dose, defined as self-reported adherence, as a covariate in order to control for this possible relationship.

Analyses for Primary Aims 1-3.

Primary Aim 1, Hypothesis 1: We hypothesize that SBIRT participants will have higher prolonged abstinence and point prevalence cessation rates compared to those in the HHC group. As stated above, our primary approach to the analysis is using multiple imputation, with clinical counselors/intake coordinators/research coordinators included in the model. We shall then use analysis of covariance, to control for any baseline differences of caregivers between conditions. In addition we will also control for motivation to quit, considered a priori as a potential covariate, using the score on the contemplation ladder. As we are stratifying on motivation to quit and caregiver gender, we will initially enter this into the model as an interaction. To address child cotinine as the 6-month outcome, we will use a t-test and then an analysis of covariance to incorporate the variables different at baseline. Incorporating the 6-week outcome values, we will use GLMM invoking GEE for the repeated

measures and also a model including covariates. This approach will be used to assess the intervention's effect on abstinence and point prevalence and child cotinine.

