Primary Aim 3, Hypothesis 3: We hypothesize that the SBIRT intervention effect on prolonged abstinence and point prevalence cessation rates will be mediated by the caregiver's perception of the risk of smoking on their child's health, or on their readiness to quit over time.^{42,66,67,69,70,99} Bivariate analyses will be used to initially examine if the variables measuring this phenomena, susceptibility, severity and benefits of quitting are associated with cessation at each time point and if there are any changes in perceived health risk from baseline to 6-months in the SBIRT versus HHC groups. We will build on the models from our primary aim to determine the association of these potential mediators. Analysis assessing these effects will be conducted using abstinence at each follow-up point as the dependent variable and testing for interactions between treatment (i.e., intervention) and the potential mediator. Additionally, we will examine the main effects of the intervention within each level of the mediator to establish whether the intervention is effective in each subgroup, acknowledging that we may be underpowered for some subgroups.

Mediation analysis: To assess whether our intervention improved cessation outcomes via the proposed mediators, we will perform mediation analyses using both the criteria of Baron & Kenny¹⁰⁰ and Holmbeck.¹⁰¹ As our outcome variables are dichotomous, we will apply the method of Huang et al.,¹⁰² which involves a system of logistic regression models and the Monte Carlo method to assess posterior distributions of the direct, indirect, and relative indirect effects. Three sets of logistic regression analyses will be performed, as the variables of interest; outcome, intervention and mediator are mainly categorical. The first 2 steps are to assess the intervention effects on the outcome and the mediator. In the third step, we will assess the relationship between each of the proposed mediators and the study outcome at each follow-up. The same 3 steps will be repeated with adjustment for potential confounders and/or moderators as determined from analysis for Hypothesis 3. The mediating variables that will be considered are: perception of child's risk from SHSe and the benefits to the child of quitting, also motivation to quit, self-efficacy. Moderating variables are household smokers, financial strain, , nicotine dependence, and prior quit attempts.

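### The mediation models do not commit to the baseline score of child-risk perception or benefits of quitting, so the indirect effect can be inflated, or falsely appear, if SBIRT moves the mediator

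*Combined protocol and SAP*

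**What the plan says.** All places are in the combined protocol and SAP.

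- **Mediation analysis (Primary Aim 3).** Three sets of logistic regressions are planned. The first two estimate the effect of arm on outcome and on mediator. For the third: "In the third step, we will assess the relationship between each of the proposed mediators and the study outcome at each follow-up". Then: "The same 3 steps will be repeated with adjustment for potential confounders and/or moderators as determined from analysis for Hypothesis 3". The method is meant to yield direct as well as indirect effects.
- **Mediators and moderators.** The mediators are perception of the child's "risk from SHSe and the benefits to the child of quitting, also motivation to quit, self-efficacy". Four moderators are also named in advance: nicotine dependence, financial strain, earlier attempts to quit and other smokers in the household. No list of confounders is given.
- **Link to Aim 1.** Under Primary Aim 3, Hypothesis 3: "We will build on the models from our primary aim to determine the association of these potential mediators". Under Primary Aim 1: "In addition we will also control for motivation to quit, considered a priori as a potential covariate, using the score on the contemplation ladder". The visit from which that score is taken is not stated.
- **Preliminary Analyses.** Variables found to differ between the arms at baseline are added as covariates.
- **Table 1.** The row "Risk Perceptions: Child; Benefits of Quitting: Child" is ticked at T0, T1 and T2, and so is motivation to quit. No row shows self-efficacy.

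The only stated Aim 3 use of the baseline risk score is a bivariate comparison, by arm, of change to 6 months. No sample size, power or alpha is given for the mediation analysis.

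**The concern.** Randomisation protects the step from arm to mediator and the step from arm to outcome. It does not protect the step from mediator to outcome. A caregiver who already saw a high risk to the child at enrolment will tend to score high at follow-up and may also be more likely to quit. Without the T0 score in the model, the follow-up score takes credit for that prior difference. Multiplied by a real SBIRT shift in the mediator, this becomes an indirect effect that is too large, or that does not exist.

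The rule in Preliminary Analyses does not catch this. It reacts to differences between arms, while this bias comes from differences between caregivers within an arm and persists when the arms are perfectly balanced. Taking the adjustment set from the Hypothesis 3 results adds a data-driven choice at the step where confounding matters most.

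At stake is the mechanism claim in Hypothesis 3, that SBIRT works through perceived child risk and motivation.

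**Working it through.** The plan gives no figure for this analysis to reproduce, so the check is a simulation anchored on its planning values.

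**Inputs from Sample Size and Power Estimates.** 300 per arm after attrition; point prevalence 6.3% (HHC) and 12% (SBIRT); prolonged abstinence 2.1% and 7%. Expected abstainers:

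- point prevalence: 300 × 0.063 + 300 × 0.12 = 54.9
- prolonged: 300 × 0.021 + 300 × 0.07 = 27.3

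**Assumptions, not in the documents.** SBIRT shift *a* = 0.3 SD (also 0 and 0.5); log-odds of quitting per SD of baseline mediator γ = 0.3 to 0.7; correlation of baseline with follow-up mediator ρ = 0.4 to 0.8; 95% intervals.

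**Model.** M1 = ρ·M0 + *a*·arm + error, with unit variance within arm. logit P(quit) = α + *c*·arm + γ·M0. M1 has no effect on quitting, so the true indirect effect is zero. The indirect effect is *a*·*b*, where *b* is the coefficient of M1 in a logistic model that also contains arm. It is tested with a Monte Carlo 95% interval.

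**Approximate size without M0.** Within arm, M0 regresses on M1 with slope ρ, so *b* ≈ ργ and the false indirect log odds ratio ≈ *a*ργ. The total log odds ratio is ln[(0.12/0.88)/(0.063/0.937)] = ln 2.03 = 0.707. At *a* = 0.3:

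- low corner: 0.3 × 0.4 × 0.3 = 0.036, about 5% of the total
- centre: 0.3 × 0.6 × 0.5 = 0.090, about 13%
- high corner: 0.3 × 0.8 × 0.7 = 0.168, about 24%

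**Simulation, continuous mediator, point prevalence, 1,500 trials per row** (last two columns: share of trials whose interval wrongly excludes zero)

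| *a* | ρ | baseline OR per SD | false indirect OR, no T0 score | no T0 score | T0 score added |
|---|---|---|---|---|---|
| 0 | 0.5–0.7 | 1.5–2.0 | 0.999–1.002 | 1–4% | under 1% |
| 0.3 | 0.5 | 1.5 | 1.062 | 27% | 6% |
| 0.3 | 0.5 | 2.0 | 1.106 | 60% | 6% |
| 0.3 | 0.7 | 1.5 | 1.089 | 45% | 6% |
| 0.3 | 0.7 | 2.0 | 1.155 | 87% | 5% |
| 0.5 | 0.5 | 1.5 | 1.106 | 29% | 6% |
| 0.5 | 0.5 | 2.0 | 1.183 | 63% | 4% |
| 0.5 | 0.7 | 1.5 | 1.154 | 51% | 5% |
| 0.5 | 0.7 | 2.0 | 1.273 | 91% | 5% |

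The approximation agrees: at *a* = 0.3, ρ = 0.7, OR 2.0 it gives 0.3 × 0.7 × 0.693 = 0.146, against a simulated mean of 0.144.

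**Full assumed range at *a* = 0.3, arm in the model.** Continuous mediator: 13% to 91%, about 50% at ρ = 0.6, γ = 0.5. The plan calls its variables mainly categorical, so the check was repeated with a median-split mediator and logistic models for both paths: 7% to 70%, about 30% at the centre. With the T0 score added: about 3% to 6%. Entering a median-split T0 score instead of the full score left up to 16%.

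**Prolonged abstinence.** Dichotomised mediator, *a* = 0.3: 5% to 42%. Continuous, *a* = 0.5, ρ = 0.7, baseline OR 2: 64% without and 5% with the T0 score.

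**The case against.** Several stronger readings are tempting, and the documents do not support them.

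- **That baseline differences by themselves create a false indirect effect.** They do not. Arm is randomised, so only the slope from mediator to outcome is biased; with no SBIRT shift the product stays at zero. The condition is likely to be met, because the staff training and the Advise component aim to raise risk perception and motivation, but no shift is quantified. With a 0.2 SD shift the central rate for a dichotomised mediator is 16%.
- **That no baseline mediator is ever adjusted for.** Motivation, one of the two mediators in Hypothesis 3, is an a priori covariate in the Aim 1 models on which Aim 3 builds. That gives no cover to perceived risk or benefits.
- **That step 3 leaves out arm.** Its sentence does not name arm, but a direct effect cannot be estimated without arm and mediator in the same outcome model. Only error rates with arm in the model are relevant.
- **That the confounder choice is circular.** The natural reading is sequential: the bivariate, interaction and subgroup analyses come first, and the mediation models take covariates from them. That is data-driven selection. Two sensible covariates, household smokers and nicotine dependence, are already named as moderators.
- **That the dissemination manual would stress the wrong component.** The plan ties the manual to the success of the intervention and to prior research, and nowhere to the mediator results.

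It can also be said that Aim 3 is framed as exploration and that the structural equation model carries perceived risk over the study period. The first limits the consequence. The second names no baseline adjustment.

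**Conclusion.** The concern holds in a conditional form. No section commits the mediation models to the T0 score of child-risk perception or benefits of quitting, and the adjustment set comes from the Hypothesis 3 results. If SBIRT moves the mediator, a mediator with no effect on quitting can still show an indirect effect. Under the assumed 0.3 SD shift this happens in roughly 30% of trials at the centre of the range for the categorical set-up nearest the plan, and in about 50% for a continuous mediator. The nominal level is nearly restored by one covariate that the trial already collects.

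These rates depend on the assumed shift, baseline association and correlation, none of which the documents give; they show sensitivity and are not the plan's error rate. Baseline adjustment does not remove unmeasured confounding, nor reverse causation when mediator and abstinence are measured at the same visit. The issue is worth correcting before analysis, but it does not touch the primary efficacy comparison.

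**What to change.** Replace the sentence on the adjusted repeat in Mediation analysis with:

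> All mediation models (arm to mediator, and mediator to outcome) include study arm and the baseline (T0) score of the mediator under test, entered as the full score, for child-risk perception, benefits of quitting and motivation. For point prevalence they also include a fixed baseline set: readiness stage, caregiver gender, nicotine dependence and household smokers. For prolonged abstinence they include arm, the mediator and its T0 score only. No confounder is selected from the Hypothesis 3 results.

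Table 1 shows no T0 measure of self-efficacy, so unless the baseline survey contains one, label that mediator's result as not baseline-adjusted.

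The short list for prolonged abstinence is deliberate: 27.3 events over 3 terms is about 9 per term, while adding four more covariates gives 27.3 / 7, about 4. Preliminary Analyses also puts a deliverer indicator in every model, so the new text should say whether that rule applies here.

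Cost: SAP wording and one to a few more model terms; no new data for the three mediators with T0 scores. As a gain, for a continuous score the T0 term cuts the residual variance of the arm-to-mediator step by ρ², that is 0.4² = 16% to 0.8² = 64% over the assumed range.

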Rationale for the use of an attention control condition. We will use an attention control condition in order to determine the efficacy of the SBIRT condition. In a RCT examining the effects of a behavioral intervention, the use of an attention control condition helps to reduce differential attention and expectancies of treatment in the intervention, and will decrease threats to internal validity.⁵⁶⁻⁵⁷ Controlling for attention will entail exposing control group participants to a meaningful clinical experience that takes as much time and provides as much contact with the CRC as the SBIRT. The use of this attention control condition is highly consistent with good clinical care, unrelated to the focus of the active intervention (i.e., smoking cessation), and likely to be perceived by families as both credible and useful. We will use a childhood obesity prevention program entitled "Let's Go! 5-2-1-0"

which is a program which has been developed and used in the outpatient clinic and school setting. This program is designed to help children and families eat healthy and be active, by recommending the following daily behaviors: 5 fruits/vegetables, no more than 2 hours of TV/computers, 1 hour of physical activity, and 0 sugary drinks.^{43,58-60} The delivery of the HHC will mirror that of the SBIRT.

HHC Protocol. After potential participants have been identified, CRCs will obtain informed consent, enroll eligible caregivers, and collect baseline data. The clinical counselors/intake coordinators/research coordinators will provide caregivers with the brief HHC intervention based on the “Let’s Go! 5-2-1-0” program^{43,58-60} and tailored on current diet and activity levels. If both caregivers are present, eligible, and wish to receive the intervention, then the clinical counselors/intake coordinators/research coordinators will provide each caregiver with the recommendations. However, only the primary caregiver (designated by the couple) will be enrolled in the study and assessed for data collection. The intervention components that will be provided are:

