We will assess for missed eligible patients by screening for, but not limited to, second hand smoke exposure complaints in children 0-18 years old through our EMR periodically, and a chart review will be completed for those not enrolled in the study to gather data about missed eligible patients. We are requesting a waiver of consent to review these patients’ charts. Data about missed patients may be used to assess screening hours as well as to assess for training needs when missed eligible patients are identified during screening time. Missed eligible data will include the patients’ encounter ID and medical record number, arrival date and time, age, who escorted the patient to the ED, triage code, spoken language, chief complaint and arrival complaint, triage start

time, departure time, disposition, city, state, and zip code, and if they were screened for another study. We will also examine the charts of all children screened during the study period to determine the sociodemographics, geographic variability, and clinical characteristics of the entire screened population. We will conduct a chart review to extract data on their demographics, zip codes, address, clinical findings, medical test results, treatment, disposition, and healthcare visit patterns. Again, we are requesting a waiver of consent to review these patient's charts. These patients cannot be consented prior to participation. However, their rights and welfare will not be affected by the data collection. The patients' data will be the same as those consented into the study and they will still receive the same care regardless of study participation.

Participant Screening, Enrollment, and Exclusion

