There is no direct benefit to the children of participants. However, there is a potential indirect benefit to the children of the caregivers in the intervention condition: if their caregivers quit or decrease their smoking habits, then their children will be exposed to lower levels of SHS. In addition, the benefit to society and research on PED-based cessation is potentially great. Since patients who are economically disadvantaged or of minority status use PEDs disproportionately, the results of this study may especially help determine the effectiveness of cessation interventions in this setting which could benefit society and the scientific community. The intervention may be disseminated to other PEDs if found to be effective. The risks this research may have for participation are very small but the potential benefit far outweighs the risk of slight embarrassment, increased time in the PED, potential loss of confidentiality, and risks of NRT.

POSSIBLE RISKS, DISCOMFORTS, OR INCONVENIENCES

There are 4 possible risks with respect to study participation:

(1) The potential to interfere with medical care that is ongoing: The study will specifically exclude caregivers of patients who are not medically stable during the ED visit. Only caregivers of patients who are stable, that is, who are not critically ill and do not require immediate treatment and intervention by the PED practitioner, will be eligible for enrollment in this proposed study. These patients are, by our triage criteria, clinically stable, not ill appearing, and not felt to be at high risk of deterioration or morbidity. All enrolled patients will be assessed, examined, and reassured by a triage nurse prior to enrollment. We will stress in the consent that participation in the study will be entirely voluntary and will not affect the care in the emergency department. Caregivers who participate may have an additional 30-40 minute longer ED visit time; however, the interviews and surveys will not be done while medical care is being delivered;

(2) Emotional discomfort when answering the issues raised by the interview: Some of our participants may feel uncomfortable answering some of the questions about their smoking habits, particularly in an ED setting where such questions are not anticipated. The consent form will clearly state that caregivers will be asked questions such as "Do you smoke?" and "How many cigarettes do you smoke a day?"

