In the final analysis, the entire theoretical model to predict outcome will be examined using structural equation modeling (SEM). The strength of SEM in examining the entire model is that this method allows for the analysis of a hypothesized pattern of directional and non-directional linear relationships among a set of latent variables (e.g., caregiver beliefs about their child's SHSe risk) and measured variables (e.g., point prevalence).¹⁰³ This approach will allow us to examine the effect of perceived risk of SHSe and perceived child benefits of quitting; we will incorporate the former as latent variables over the study period. We will also be able to examine the relative relationship of caregiver's beliefs and readiness to quit with the outcome of cessation.

Analyses for Secondary Aim 1. Working closely with [name] (health services and economic consultant), we will collect the cost data needed to conduct a cost analysis of the SBIRT intervention. The cost inventory may include costs and charges from the baseline PED visit and hospitalization (if the child is hospitalized) and from SHSe-related PED visits or hospitalizations for the period 6 months before and 6 months after the baseline visit. The cost inventory will also include data collected from CRCs and clinical counselors/intake coordinators/research coordinators in both conditions about cessation-related activities and expenses, self-reported abstinence, and use of all tobacco products at each follow-up. Cost inputs will include staff time for tobacco screening, chart flagging, cessation counseling, giving informational materials and NRT, and referral to the QL, smokefreeTXT, or smokefree.gov. To determine costs of SHSe-related PED visits and hospitalizations

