at CCHMC, clinical and cost/charges data will be collected from hospital records for the 6 month period before and after baseline for SHSe-related illness PED visits and hospitalizations such as asthma, and compiling the associated costs. We anticipate that the main cost component for intervention delivery will be the minutes the clinical counselors/intake coordinators/research coordinators spends in counseling. Although the intervention will occur during the time the patient is waiting for care, the time the clinical counselor/intake coordinator/research coordinator spends represents an opportunity cost of other alternative ways of spending this time with caregivers and should be tracked for inclusion in the cost-effectiveness analysis. Because the intervention will be delivered during visits of normal length, we do not anticipate that PEDs will incur any other overhead costs (e.g., facilities) due to adoption of the intervention. It is possible that a final version of the SBIRT will require changes in CMS billing codes to accommodate payment for the service. It is premature to determine this now, and establishment of the evidence-base of the intervention is required to provide a justification for a full review of coding options. As we conduct the cost analysis, we will conduct a preliminary review of coding options in anticipation of continued empirical work with the SBIRT to optimize its adoptability in PED settings.

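### The cost analysis assumes no overhead beyond staff time because visits keep their normal length; the risk section says visits may run 30-40 minutes longer, and the two are not reconciled

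*Combined protocol and SAP*

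**What the plan says.** The section on analyses for Secondary Aim 1 builds the delivery cost from listed inputs: "Cost inputs will include staff time for tobacco screening, chart flagging, cessation counseling, giving informational materials and NRT", plus referral to the cessation services. It expects counselling minutes to be the main component and treats them as an opportunity cost to be tracked, even though the family is waiting anyway. It then says: "Because the intervention will be delivered during visits of normal length, we do not anticipate that PEDs will incur any other overhead costs". The sentence gives facilities as its example of overhead and ties the statement to adoption of the intervention.

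The section on possible risks, discomforts and inconveniences says, under interference with medical care: "Caregivers who participate may have an additional 30-40 minute longer ED visit time". It adds that "the interviews and surveys will not be done while medical care is being delivered". The risk-benefit text just before it lists "slight embarrassment, increased time in the PED, potential loss of confidentiality" among the risks of taking part.

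The rationale for the attention control requires an experience that "takes as much time and provides as much contact with the CRC as the SBIRT", and adds: "The delivery of the HHC will mirror that of the SBIRT".

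Costs and charges of the baseline visit are to be evaluated under the clinical and cost data item of the measures. The Secondary Aim 1 section says only that the cost inventory may include them. Neither place says whether those figures vary with time spent in the department.

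**The concern.** The exclusion of overhead rests on a single stated reason, that visits are not lengthened. The only figure for visit length in the document points the other way. No section divides the 30-40 minutes between research procedures and the intervention, and no analysis of length of stay or sensitivity analysis of the premise is planned.

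Secondary Aim 1 is meant as groundwork for a later full cost-benefit analysis, and the protocol foresees dissemination to other departments. If SBIRT lengthens visits at all, the occupied department time is a cost to the adopting site that the analysis would not show. The plan already counts counsellor minutes as an opportunity cost, and the same reasoning applies to any department time that delivery adds.

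**Working it through.** The plan has no derived figure to reproduce here; the 30-40 minutes is simply stated. The check sets the passages side by side and then bounds the size.

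**Scope of the two statements**

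| | Risk section | Secondary Aim 1 section |
|---|---|---|
| Setting | Taking part in the trial, either arm | Adoption of SBIRT in routine care |
| Activities | Consent, tablet survey and possibly saliva, hand-wipe and urine samples, as well as the intervention | Counselling, materials, NRT and referral, during waiting time |
| Effect on visit length | May be 30-40 minutes longer | None expected |

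The statements are compatible if research procedures account for all the added time. They conflict if any of it comes from SBIRT. The documents do not say which holds.

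**Inputs**

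- SBIRT arm: 375 caregivers (750 randomised to two groups; the power section uses 375 per group).
- Added visit time if the risk-section figure applies: 30 to 40 minutes.
- Share due to SBIRT itself: not given. Assumed range 0% to 100%.

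**Added department time in the SBIRT arm** = 375 × minutes / 60

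- All 30 minutes due to SBIRT: 375 × 30/60 = 187.5 hours.
- All 40 minutes due to SBIRT: 375 × 40/60 = 250 hours.
- None due to SBIRT: 0 hours.

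The range the documents support is therefore 0 to 250 hours. Per visit that is 0 to 40/60 = 0.67 hours, and each minute attributable to SBIRT is worth 375/60 = 6.25 hours across the arm. Converting hours to money needs a cost per department hour, which the documents do not give.

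**Whether the trial could test the premise**

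Let each arm add *a* minutes to an underlying visit length *L*, as the time-matched design intends. The expected SBIRT minus HHC difference is (L + a) − (L + a) = 0, whether *a* is 0, 30 or 40. The randomised comparison carries no information about *a*. The same limit applies to a between-arm comparison of baseline-visit costs.

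**The case against.** The strongest reply is that the two passages describe different things. A risk disclosure about a trial visit, hedged with the word may, says little about routine use, where consent, the research survey and sampling would fall away. The plan also gives a reason for expecting no added time: counselling takes place while the child waits to be seen, and the protocol argues at length that such waits are long and unavoidable. Counselling that fits inside the wait adds nothing to length of stay. This stands. It is why the lower end of the range is zero. It does not show that zero is the right single value, because the overlap is asserted and not measured.

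A reader might infer that SBIRT itself adds 30-40 minutes, so that 187.5 to 250 hours are left out and the cost of SBIRT is understated. The documents do not support this, since the figure is never attributed to the intervention. Understatement is possible but not shown.

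A reader might also infer that the plan misuses the control arm to estimate delivery cost. It does not. Delivery is costed directly from staff time and listed inputs, and the between-arm comparison in Secondary Aim 1 concerns smoke-exposure-related visits and hospitalisations. The time matching matters only because it closes off one way of checking the premise.

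Finally, baseline-visit costs may enter the inventory, and the plan states an expectation about overhead, not a rule against counting it. Both are fair. Neither supplies an estimate of added time.

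**Conclusion.** The concern holds as an unreconciled premise. The cost analysis takes overhead beyond staff time as zero on the ground that visits are of ordinary length. The risk section allows for longer visits, and nothing in the plan settles how much of the difference belongs to SBIRT. The added time in the SBIRT arm lies between 0 and 250 hours, assuming 375 caregivers, at most 40 minutes each, and an unknown share due to the intervention. No money figure can be derived from the documents.

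The efficacy analyses under the primary aims are unaffected. Secondary Aim 1 is itself preparatory, so this is a minor point, but one that is cheap to correct and that changes how firmly its cost figure can be stated.

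**What to change.** 1. Reconcile the overhead sentence in the Secondary Aim 1 section with the visit-time statement in the risk section. Say which activities the 30-40 minutes covers and which of them would remain on adoption.
2. Report the intervention minutes, which the plan already says should be tracked, separately from time spent on research procedures. Where research minutes were not logged (no section says that they were), say so and rely on the range in step 3.
3. Replace the fixed zero with a sensitivity analysis that costs 0 to 40 added department minutes per SBIRT visit, for example in steps of 10, with the hourly cost and its source stated.

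A comparison of length of stay with non-enrolled children would be optional and exploratory only. The section on missed eligible patients lists arrival time and "departure time, disposition, city, state, and zip code" for those patients, but the corresponding times for enrolled children are not in the listed clinical and cost data and would have to be extracted. The comparison would also be non-randomised.

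The cost of the change is a short text revision and a small added analysis. The resulting cost estimate will be wider and slightly less favourable to SBIRT. Recruitment, randomisation and the primary analyses stay as they are.
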